This research will be done in three phases involving young adults, ages 18-34, susceptible to WTS (i.e., nonusers who do not oppose trying WTS)²⁷ or engage in WTS at least monthly. Phase 1 concerns selecting text and graphic health warnings that can strongly influence beliefs and feelings about personal risk and intention to quit or try WTS. We will create, refine, and select text and graphic health warnings in four domains: 1) longer-term health effects, 2) shorter-term health effects, 3) addictiveness, and 4) types and levels of toxicant exposures. We will also select the most appealing waterpipe product and social allure ads themes that entice young adults to engage in WTS. The top two text and graphic health warnings in each domain and the top two product and social allure ads within each theme will be used for Phase 2. In Phase 2, using the online consumer crowdsourcing platform Turkprime²⁸, susceptible nonsmokers and smokers (N=1000 per group) will be randomized to review ads with: 1) no health warnings, 2) text only health warnings, or 3) text + graphic health warnings. Nested within Arms 2 and 3 is health warning domain and ad theme. Reactions to ads will include ability to grab attention, cognitive and affective beliefs and attitudes toward each ad and ad appeal to engage in WTS. Main outcomes will include perceived risk and worry about harms (i.e., risk appraisal), attitudes

toward WTS, and intention to try or quit WTS. At a two-week follow-up, we will reassess these main outcomes, WTS, and recall of ad content. In Phase 3, using a new sample of susceptible nonsmokers and waterpipe tobacco smokers (N=100 per group), we will conduct an eye-tracking laboratory study to examine whether warnings evoke changes in attention that mediate changes in risk attitudes. The *primary aims* are to:

AIM 1 (Phase 1): Develop, pilot test, and select text and graphic health warnings in four domains (i.e., long/short-term health effects, addiction, type and level of toxicant exposures) that most dissuade WTS as well as select waterpipe tobacco product ads (themes of flavored tobacco, waterpipe apparatus) and social allure ads (four themes of eroticism, exoticism, social acceptance, and occasion appropriate) that most entice WTS.

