theme selected by each panel. Ads will be counterbalanced in a Latin-square design. For waterpipe product ads, participants will be randomized to review either the four tobacco- or four waterpipe apparatus-themed ads counterbalanced in a Latin-square design. Reactions to the social allure and waterpipe product ads will mirror those of the warnings. These will include: extent ad grabbed attention⁹⁶, credibility, relevance, fear appeal, extent ad influenced cognitive and affective beliefs about WTS¹⁰⁰, global attitude about ad⁹⁹, effort reviewing the ad, and extent ad *enticed* them to want to smoke (average of 2 items about ad making WTS more appealing and making them want to smoke 1=none at all, to 7=a great deal). They will rate extent each ad captured the social allure/product themes. Responses will be averaged for each ad within theme. *The top two ads within each social allure theme (8 total), and the top two within each product ad theme (4 total), with the highest mean score on enticing them to “want to smoke” waterpipe will be chosen for Phase 2.* All 24 ads will be used as stimuli for Phase 3.

Phase 2 Procedures:

Tests of ads with or without health warnings. Using Turkprime, we will recruit online 1000 waterpipe tobacco smokers and 1000 susceptible nonsmokers (\$2.00 payment). After screening and collecting baseline demographic and tobacco use data (e.g., cigarettes), participants will be stratified and randomized to review ads with or without health warnings. After obtaining participants' reactions to ads, we will assess key study constructs. All participants will complete a two-week follow-up.

Interventions. Participants will be stratified by sex and use of other tobacco products (no/yes) and then randomized in a 1:2:2 ratio to one of three arms: 1) no health warnings (i.e., review ads only – control); 2) text health warnings only; or 3) text + graphic health warnings. Nested within Arm 2 and 3 will be both ad themes (six total) and health warning domains (four total). Each arm is discussed below.

- *Control arm (N = 200).* Participants will be randomized with equal probability to one of the six ad themes (2 from product, 4 from social allure). They will view in counterbalanced order the two ads chosen for that theme from Phase 1 – no order effects are expected. They will not receive any warnings. (N ≈ 33 per cell).

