- *Text only health warnings (N = 400).* Ad theme selection will occur as with the control arm. Nested also as a between-subjects factor will be warning domain. Participants will see two text warnings from the same domain randomly assigned to the two ads within the same theme with ad order counterbalanced. Hence, this arm is primarily a 4 (warning domain: long-/short-term health effects, addiction, toxins) X 6 (ad theme: eroticism, exoticism, social acceptance, occasion appropriate, (flavored) tobacco, waterpipe apparatus) X 2 (ad order: A1A2 vs A2A1) between-subjects factorial design. Expecting no order effects, there are 24 main cells (N ≈ 32 per cell combining populations).
- *Text plus graphic health warnings (N = 400).* This arm is procedurally identical to the text only arm. The exception is that the two graphic warnings would be randomly added to the text warning in the same domain; thus, graphs are matched to the text warnings by health domain. (N ≈ 32 per cell combining populations).

Post intervention assessments. We will assess participants' reactions to each ad. *We will not assess reactions to warnings specifically; doing so may unduly bring attention to them.*

Reactions to warnings will have been obtained from Phase 1 and 3. After responding to the last ad, and aligned with the Message Impact Framework⁷², we will assess participants' knowledge of harms¹⁰², risk appraisals¹⁶, cognitive and affective beliefs and attitudes about WTS100, and intentions to quit/willingness to try WTS (4-item scale)¹⁴. We've used versions of these measures with $\alpha > .70$.

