We will use 90% power at .01 level of significance (two-tailed) for univariate tests and contrasts. Possible covariates obtained within the survey will include: race, sex, education, use of other tobacco products and among smokers, WTS frequency and level of addiction to WTS. Missing data will multiply imputed¹⁰⁵ as appropriate after checking missing randomness¹⁰⁶. For H2A and H2B, factorial MANOVAs will be conducted using SAS Proc GLM for all outcomes simultaneously. For H2A, if the omnibus multivariate test is significant at a .05 level, rather than .01, for the primary outcomes (risk appraisals, beliefs/feelings about WTS, global attitude about WTS, and intention to quit/willingness to try WTS), we will perform post-hoc univariate tests for each outcome at a .01 level for comparisons among: (a) ads without health warnings (control arm), with text warning only, and with both text + graphic health warnings; (b) four health warning domains; (c) six ad themes; d) two study populations; and interactions of a-d. Noteworthy, the interactions will be incomplete due to lack of health warnings in the control arm. Thus, Type IV sum of squares will be used to address empty cells. For H2B, the same statistical methods will be conducted as with H2A, using reactions to ads as the main outcomes. For H3, we have several mediators (reactions to ads). We will use the SAS Macro by Preacher and Hayes¹⁰⁷ to test multiple mediation effects in each study population. This approach address both multiple mediators simultaneously as well as multi-categorical variables¹⁰⁸ such as warning domains as proposed herein.

Importance / Value:

Waterpipe tobacco smoking (WTS) is becoming widespread in the United States among young adults^{17,18}. Increases in WTS are partly due to advertisements (ads) that entice young adults to engage in WTS^{19,20}. Often devoid of health warnings^{22,23}, waterpipe product and social allure ads likely mislead young adults to believe WTS is safe, promoting experimentation with WTS and reducing the desire to quit among users^{19,24}. Thus, as shown with cigarette health

warnings¹, designing effective text and graphic (i.e., pictorial) warnings is vital to curbing the effects of these ads.

Risks / Benefits:

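### Nonsmokers are screened on openness to trying WTS before randomization, but that answer is not listed as a covariate for the willingness-to-try outcome, so precision is likely lost

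*Combined protocol and SAP*

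**What the plan says.** *Entry.* Under Study Design, the susceptible group is defined as "nonusers who do not oppose trying WTS". Inclusion Criteria repeats that participants must be susceptible or current smokers. Neither section gives the screening items, their response scale or their scoring.

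*Timing.* Phase 2 Procedures states: "After screening and collecting baseline demographic and tobacco use data (e.g., cigarettes), participants will be stratified and randomized". The screen therefore comes before randomization and before any ad. On allocation, the Interventions paragraph says: "Participants will be stratified by sex and use of other tobacco products (no/yes) and then randomized in a 1:2:2 ratio". Susceptibility is not a stratification factor.

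*Outcome.* Under Post intervention assessments, intention to quit (smokers) or willingness to try (nonsmokers) is measured after the last ad on a four-item scale. The statistical section names it among four primary outcomes, with risk appraisals, beliefs and feelings about WTS, and global attitude. It is asked again at two weeks. No pre-exposure measurement of any primary outcome is described.

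*Covariates and model.* The statistical section says "Possible covariates obtained within the survey will include" and then lists "race, sex, education, use of other tobacco products and among smokers, WTS frequency and level of addiction to WTS". For H2A and H2B, "factorial MANOVAs will be conducted using SAS Proc GLM for all outcomes simultaneously", with study population as one of the factors. The H3 mediation models are run separately in each population. Missing data are to be multiply imputed where appropriate.

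**The concern.** The question that admits a nonsmoker and the question later analysed as an outcome both concern openness to trying WTS. A pre-exposure answer on nearly the same content is usually among the stronger predictors of the post-exposure answer, and the trial has to ask it anyway. The covariate list nevertheless gives smokers two WTS-specific baseline measures and nonsmokers none.

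At stake is the width of the intervals for willingness to try in the 1,000 nonsmokers, both immediately and at two weeks. The protocol expects 60% to 70% to complete follow-up, which is about 600 to 700 nonsmokers if the rate is the same in both populations. The decision also has a deadline: graded answers not saved at screening cannot be recovered.

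A smaller, related gap is that H2 uses one model for both populations while some covariates exist in only one of them. The plan does not say how such covariates are coded.

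**Working it through.** **Inputs from the document.** Phase 2 has 1,000 smokers and 1,000 susceptible nonsmokers. Within each population, 200 are in control, 400 in text and 400 in text + graphic. Univariate tests and contrasts use two-sided α = .01. The power design is 3 × 4 × 6 × 2 = 144 cells.

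**Assumed inputs.** These are the correlation r between graded screening answer and later willingness, and the standardized difference d between arms. The document gives neither.

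**1. The plan's own figure.** Use the noncentral F with λ = f²N, numerator df = (3−1)(4−1)(6−1)(2−1) = 30, denominator df = N − 144, α = .01 and power .90. The required N is 3,934, 657 and 289 for f = 0.10, 0.25 and 0.40, exactly as stated. No covariate enters that calculation, so this point corrects no stated number.

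**2. Residual variance in nonsmokers.** Adjustment multiplies the residual variance by 1 − r². The equivalent sample-size factor is 1/(1 − r²).

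| r (assumed) | 1 − r² | Variance reduction | 1/(1 − r²) |
|---|---|---|---|
| 0.3 | 0.91 | 9% | 1.10 |
| 0.4 | 0.84 | 16% | 1.19 |
| 0.5 | 0.75 | 25% | 1.33 |

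**3. Power for one warning arm against control, nonsmokers only (400 vs 200).** Power ≈ Φ( d / √[(1 − r²)(1/200 + 1/400)] − 2.576 ), where √(1/200 + 1/400) = 0.0866.

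For d = 0.25 and r = 0: 0.25/0.0866 = 2.887; 2.887 − 2.576 = 0.311; Φ = 62.2%.

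| d (assumed) | r = 0 | r = 0.3 | r = 0.5 |
|---|---|---|---|
| 0.20 | 39.5% | 43.8% | 53.6% |
| 0.25 | 62.2% | 67.4% | 77.6% |
| 0.30 | 81.3% | 85.4% | 92.3% |

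**4. The same contrast with populations pooled (800 vs 400).** The covariate acts in the nonsmoker half only, so average residual variance is [1 + (1 − r²)]/2, which is 0.955 at r = 0.3 and 0.875 at r = 0.5. With d = 0.20 (assumed), power goes from 75.5% to 77.8% and 82.0%.

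**5. What form the variable must take.** Every enrolled nonsmoker passed the screen, so a pass/fail flag is constant among them and redundant with the population factor. In a simulated data set with the planned arm sizes and a model with arm, population, their interaction and the flag, the design matrix has rank 6 of 7 columns. The gain is then zero.

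**6. Whether population-specific covariates can be used in the pooled model.** In the same model, a smoker-only covariate set to zero for nonsmokers keeps all 2,000 rows and full rank (7 of 7). The same coding works in reverse for susceptibility.

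**The case against.** The case against has four parts, and most of it stands.

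- The list is headed as possible covariates. It commits to none and excludes none, so the accurate statement is that susceptibility is not listed.
- The overlap between screen and outcome is inferred from similar wording. The document shows no items and does not say a graded answer exists or is kept.
- The benefit falls mainly on one of four primary outcomes in one of two populations. Selecting on the screen narrows the range of answers, which pushes r down.
- With randomized arms there is no validity problem, and choosing covariates for precision is partly a matter of judgement.

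These parts limit the size of the point without removing it. The screen must be asked, it precedes randomization, and nothing in the plan secures its use.

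A reader might infer something stronger: that the smoker-only covariates break the pooled analysis, either because Proc GLM drops all 1,000 nonsmokers for missing values or because imputation supplies addiction levels to people who do not smoke. The document does not support this. It restricts those two covariates to smokers, calls the whole list possible, and imputes only where appropriate. Nowhere does it say they enter the pooled model as blanks. They can be used directly in the H3 models, which are run by population, and step 6 shows they can be coded into the pooled model without losing a row. What remains is an unstated coding rule.

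**Conclusion.** The point holds as a modest, inexpensive gain in precision. Nonsmokers' openness to trying WTS is established before randomization, overlaps in content with a primary outcome, and is neither a stratification factor nor a listed covariate.

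With r between 0.3 and 0.5, adjustment would cut residual variance for willingness to try in nonsmokers by 9% to 25%. In the nonsmoker-only contrast at d = 0.25, power would rise by about 5 to 15 percentage points; in the pooled contrast at d = 0.20, by about 2 to 6.5 points. Both r and d are assumptions. The gain is zero if the screen is stored as yes/no.

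Two readings go too far. The omission does not bias the comparison of arms, because randomization protects it. Nor does the plan as written lose half the sample or impute meaningless values; it leaves the handling of population-specific covariates unstated.

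**What to change.** 1. Record and retain the graded answers to the susceptibility screen for every Phase 2 nonsmoker, in addition to the eligibility result.
2. Name the resulting score as a prespecified covariate for nonsmokers in the H2 models and the two-week analyses.
3. State the coding rule for pooled models: each population-specific covariate (susceptibility for nonsmokers; WTS frequency and addiction level for smokers) is centred within its own population and set to zero in the other, with population kept as a factor. It is not imputed for people to whom it does not apply.

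The cost is one or two sentences in the statistical section and retention of a screening variable. If the screen is currently a single yes/no item, item 1 also means asking it with graded responses. That has to be settled before Phase 2 enrolment.

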We consider this study to involve very minimal risk. Some participants may become alarmed of learning the potential health implications of waterpipe tobacco smoking and the potential for addiction. This may be especially alarming among smokers of other tobacco products (e.g., the perception of the compounding of health risks and potential for addiction using several products). For others, learning of these issues may reinforce existing knowledge.

The benefits of participation, other than the fiscal compensation for completing the entire study (see below), are that participants gain a better understanding of health effects of WTS. The ultimate study goal, and hence benefit to study participants, is to equip them with knowledge that they can use to curb the persuasive appeal of WTS ads, prevent further experimentation with waterpipe tobacco, and achieve cessation to avoid future harm. The benefits of this study also include findings that may lead to policy changes in the regulation of WTS ads from commercial establishments, such as those posed by the FDA.

Data Safety and Monitoring:

This study neither involves the testing of pharmacologic agents nor therapeutic treatments. The primary goal of this study is to examine how the provision of text only or text + graphic health warnings, or lack therefore, on social allure and waterpipe tobacco product ads influence risk appraisals, cognitive and affective beliefs and attitudes about waterpipe tobacco smoking (WTS) and intentions to quit/willingness to try WTS among waterpipe tobacco smokers and susceptible nonsmokers, respectively. This study also examines whether any effects are mediated by reactions to the ads, with a subcomponent to study in more detail attentional factors as potential mediators through use of eye-tracking. Thus, it is classified as a Type 3 Study (Non-therapeutic, non-physical intervention), a minimal risk level study that dictates annual review by the Duke Cancer Center Scientific Monitoring Subcommittee for scientific progress and IRB compliance (*The overall Duke DSMB plan follows the specific details regarding DSMB procedures that will be followed by the research team*).

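### Quit intention (smokers) and willingness to try (nonsmokers) share one primary-outcome slot in a pooled model, with opposite wanted directions and no stated scoring direction or common metric

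*Combined protocol and SAP*

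**What the plan says.** All references are to the combined protocol and SAP.

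- **Model.** Under Sample Size (power calculations) and statistical considerations, for H2A and H2B, "factorial MANOVAs will be conducted using SAS Proc GLM for all outcomes simultaneously". The gate applies "if the omnibus multivariate test is significant at a .05 level, rather than .01, for the primary outcomes". After it, "we will perform post-hoc univariate tests for each outcome at a .01 level for comparisons among: (a) ads without health warnings". The list of comparisons ends with "d) two study populations; and interactions of a-d". Population is therefore a factor inside one model.
- **Outcome.** The list of primary outcomes closes with "global attitude about WTS, and intention to quit/willingness to try WTS". That is one entry with two measures.
- **Who answers what.** Data Safety and Monitoring gives the assignment: "intentions to quit/willingness to try WTS among waterpipe tobacco smokers and susceptible nonsmokers, respectively". Quit intention belongs to smokers, and willingness to try belongs to susceptible nonsmokers.
- **Measurement.** Phase 2 Procedures, post-intervention assessments, says only "intentions to quit/willingness to try WTS (4-item scale", with a citation and a general remark on reliability. It gives no scoring direction, reversal or standardisation.
- **Stratified analysis.** Only the H3 mediation analysis is stated to be run in each population.

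**The concern.** The study wants smokers to become more inclined to quit and nonsmokers less inclined to try. On scales where higher means more of the named construct, a successful warning moves the outcome up in one half of the sample and down in the other. The pooled arm main effect averages the two halves, so the benefits subtract. The arm-by-population term measures half the signed difference, so it grows when both groups benefit.

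At stake is the only intention measure among the four primary outcomes. An arm effect present in both groups could fail its own test, and similar benefit could be read as a difference between populations. That second risk matters because Aim 2 sets out to explore how population influences these outcomes.

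A separate problem does not depend on coding. Comparison (d), smokers against nonsmokers, on this outcome compares quit intention with willingness to try.

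**Working it through.** **1. The plan's own figure.** The power design is 3 × 4 × 6 × 2 = 144 cells. The highest-order interaction has 2 × 3 × 5 × 1 = 30 numerator df. With a noncentral F, λ = f²N, denominator df N − 144, α = .01 and power .90, the required N is 3934, 657 and 289 for f = 0.10, 0.25 and 0.40. This matches the document exactly. It confirms that the power calculation treats population as a factor in one model.

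**2. Inputs for the check.**
- From Phase 2 Procedures: 1000 per population, allocated 1:2:2. That gives 200/400/400 per population and 400/800/800 pooled.
- From the statistics section: α = .01 for univariate tests ("We will use 90% power at .01 level of significance (two-tailed) for univariate tests and contrasts").
- Assumed, because the document gives no SD or expected difference: both warning arms differ from control by the same d, in SD units, within each population.
- Filled cells: control 6 × 2 = 12, plus two warning arms of 24 × 2 = 48 each, total 108. Error df = 2000 − 108 = 1892.

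**3. Formula.** For the three-arm test with a pooled effect d, the overall mean is 0.8d. So λ = N[0.2(0.8d)² + 0.8(0.2d)²] = 0.16Nd². Power is the upper tail of a noncentral F with 2 and 1892 df beyond the .01 critical value. For the arm main effect, d is the mean of the two population effects. For the arm-by-population term, d is half their difference.

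**4. Equal benefit of 0.25 SD.**
- As named: main effect d = (0.25 − 0.25)/2 = 0, so λ = 0 and the rejection rate is 1%, the α level.
- Aligned: d = 0.25, λ = 0.16 × 2000 × 0.0625 = 20, power 94%.
- Interaction as named: d = (0.25 + 0.25)/2 = 0.25, λ = 20, so it rejects 94% of the time. Aligned, it rejects at about 1%.

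**5. Unequal benefit, 0.40 SD in smokers and 0.20 SD in nonsmokers.**
- As named: d = (0.40 − 0.20)/2 = 0.10, λ = 3.2, power 15%.
- Aligned: d = 0.30, λ = 28.8, power 99%.

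**6. Range.** Aligned power is 76% at 0.20 SD and 99% at 0.30 SD. A simulation (2000 runs, 3 arms × 2 populations) with equal effects of 0.20, 0.25 and 0.30 SD in opposite directions gave main-effect rejection of 1.0–1.2% and interaction rejection of 75%, 95% and 99%. For text against control alone, effects of +0.30 and −0.20 give 4% as named and 93% aligned; +0.30 and −0.10 give 17% and 76%. The loss does not need exact symmetry.

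**7. Within one population.** With N = 1000 and d = 0.25, λ = 10 and the three-arm test at .01 has about 61% power.

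These univariate figures approximate the full model with Type IV sums of squares.

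**The case against.** **Nothing says that raw scores are pooled.** A reader might infer that the plan will cancel a real effect and create a false interaction. The document does not support that. It is silent on scoring for this scale, the cited instrument is not available here, and aligning item direction is routine. This stands, and the power figures are conditional on scoring as named. It does not remove the point: the direction of a primary outcome should be fixed in advance, and the text as written gives one slot to two measures with opposite wanted directions.

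**The interaction test would expose a crossover.** A reader might infer that the effect could be missed entirely. That is also too strong. The plan tests arm by population on each outcome, and under raw coding with equal 0.25 SD benefit that test rejects about 94% of the time. The cell means would show quit intention rising and willingness falling. What remains is that the main-effect test fails and the significant interaction invites the wrong reading.

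**The omnibus gate.** One might infer that the cancelled outcome also damages the multivariate test. No material harm is shown. The gate takes four outcomes at .05, and three do not share the reversal. In a simulation with 0.25 SD on those three, full cancellation on the fourth and correlations of 0 to 0.7, the gate passed in essentially every run.

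**Zero is the extreme case.** Full cancellation needs equal standardised effects, and all effect sizes here are assumed. This stands; unequal effects give attenuation, as shown.

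**Conclusion.** The point holds in conditional form. The plan enters two constructs with opposite wanted directions as one primary outcome in a model pooling both populations, and fixes neither direction nor metric. If scored as named, the pooled arm test on that outcome falls to about 1% power with equal 0.25 SD effects (94% aligned), or to 15% with 0.40 and 0.20 SD (99% aligned), and a coding-driven interaction appears. These sizes rest on assumed effects that are the same in both warning arms, and on the planned 400/800/800.

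One part is unconditional: even with aligned scores, the population main effect on this outcome compares different constructs.

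The reach is limited to one of four primary outcomes. It should be settled before the outcome data are analysed.

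**What to change.** Add to the H2A paragraph of the statistics section:

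> For intention to quit/willingness to try, willingness to try is reverse-scored so that higher means less inclined to WTS in both populations, and scores are standardised within population before any pooled arm test. The arm effect is also reported within each population. The population main effect is not tested or interpreted for this outcome.

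This takes a short addition and a recode, with no change to design, sample or the other outcomes. It has three costs:

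- Standardising within population sets both population means to zero, so comparison (d) is lost for this outcome.
- Reversal corrects the sign but does not make the constructs equivalent, so the arm-by-population term still needs cautious reading.
- The within-population tests are weaker, at about 61% power for 0.25 SD against 94% pooled and aligned.

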Total Participant Accrual:

3,000

Duration of Accrual:

6 months

Duration of Study:

16 months

Sample Size (power calculations) and statistical considerations:

Power calculations were conducted on factorial MANOVAs for H2A and H2B, and general linear models for H3 (mediation). There are no established programs to calculate required sample size for multiple mediations; however, general linear models are the core procedures for multiple mediations. As stated, the factorial design is incomplete; to be conservative, this power analysis was based on a complete 3 (study arms) x 4 (health domains) x 6 (ad themes) X 2 (populations) design. Using G*Power¹⁰⁹ the required total N for detecting an effect size (small: $f = 0.10$ or $f^2 = 0.02$; medium: $f = 0.25$ or $f^2 = 0.15$; large: $f = 0.40$ or $f^2 = 0.35$) with 90% power, two-tailed, with $\alpha = .01$ for all main and interaction effects is 3934 for small, 657 for medium, and 289 for large effects. We are well-powered to detect moderate effect sizes.

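### Each warning domain and ad theme rests on only two selected items and is tested against between-person error alone, so a difference between particular items can be declared a domain or theme effect

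*Combined protocol and SAP*

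**What the plan says.** Under Study Design, Phase 2 takes forward "The top two text and graphic health warnings in each domain and the top two product and social allure ads within each theme". The Phase 1 pilot section ranks the warnings on mean efficacy separately for smokers and susceptible nonsmokers. It does not make clear whether this gives one shared pair per domain or one pair per population.

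Under Phase 2 Procedures, each participant is assigned one theme and views both of its ads. In the two warning arms each participant is also assigned one domain: "Participants will see two text warnings from the same domain randomly assigned to the two ads within the same theme". The text plus graphic arm adds the domain's two graphics to its texts. Reactions are recorded for each ad. Risk appraisals, beliefs, attitudes and intentions are measured once, after the last ad.

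Under Sample Size and statistical considerations, "factorial MANOVAs will be conducted using SAS Proc GLM for all outcomes simultaneously". The univariate tests follow "if the omnibus multivariate test is significant at a .05 level, rather than .01", and they cover arms, "b) four health warning domains; (c) six ad themes", populations and interactions. The standard for them is stated as: "We will use 90% power at .01 level of significance (two-tailed) for univariate tests and contrasts". The section contains no term for individual ads or warnings, no item-level sensitivity analysis and no limit on generalising beyond the items chosen.

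**The concern.** Aim 2 asks how the domain of a warning and the theme of an ad influence the outcomes. That is a question about categories. With two items per level, seen by everyone at that level, the planned test shows whether one chosen pair did better than another. For the outcomes measured once (H2A), the pair is completely confounded with its category.

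The number of participants does not help. With 333 to 400 people per level, person-level error is small, so even modest item differences become significant. The .05 omnibus test gives no protection, because item variation inflates it as well. At stake are statements that one domain warns better or one theme entices more. The mediation analysis (H3) also uses warning domain as a predictor, and the protocol expects its findings to inform regulation.

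**Working it through.** **1. The plan's own figure.** The power section assumes a "complete 3 (study arms) x 4 (health domains) x 6 (ad themes) X 2 (populations) design", 90% power and alpha .01. That design has 3 × 4 × 6 × 2 = 144 cells, and its highest-order interaction has 2 × 3 × 5 × 1 = 30 df. With noncentrality N·f² and error df N − 144, a fixed-effects F test at f = 0.10, 0.25 and 0.40 needs N = 3934, 657 and 289. The plan states that the required total "is 3934 for small, 657 for medium, and 289 for large effects", which is an exact match. The arithmetic is sound, and its only source of error is between persons.

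**2. Participants per level.** There are 1000 people per population, allocated 1:2:2, so 200, 400 and 400 per arm in each population.
- Domain: 2 populations × 2 warning arms × 400 = 1600 people; 1600 / 4 = 400 per domain.
- Theme: 2000 / 6 ≈ 333 per theme.

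**3. Rejection rate with no true category difference.** Let s be the SD of item effects in units of the residual person SD (an assumption), m the number of items per level and n the people per level. A level mean then has variance 1/n + s²/m, where the planned test assumes 1/n. The F statistic is inflated by R = 1 + n·s²/m, and the true rejection rate is P(F > F_crit / R).

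The .01 critical values are 3.795 for domain (3 df) and 3.029 for theme (5 df), with 1500 error df. Using 1892 (2000 people less 108 filled cells) leaves the whole-percent results unchanged. Worked example for domain, s = 0.10, m = 2: R = 1 + 400 × 0.01 / 2 = 3.0; 3.795 / 3.0 = 1.265; P = 28.5%.

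If the warning pairs differ by population, a pooled domain mean averages four items, so m = 4. At s = 0.10, R = 1 + 400 × 0.01 / 4 = 2.0 and P = 12.8%.

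| Assumed s | Domain, one shared pair | Domain, pair per population | Theme |
|---|---|---|---|
| 0 | 1.0% | 1.0% | 1.0% |
| 0.05 | 5.6% | 2.8% | 5.8% |
| 0.10 | 28.5% | 12.8% | 33.9% |
| 0.15 | 55.8% | 32.1% | 67.1% |

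An s of 0.10 is about 1% of outcome variance (0.01 / 1.01). The table treats text warnings as the items and ignores extra variation from graphics.

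**4. One strong item among otherwise equal ones.** An item stronger by d shifts its level mean by d/2, so the noncentrality is n·(d/2)²·(1 − 1/k) for k levels. For domain at d = 0.5: 400 × 0.0625 × 0.75 = 18.75. The chance of a significant main effect at d = 0.2, 0.3 and 0.5 is 11%, 33% and 89% for domain, and 7%, 23% and 78% for theme.

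**5. Effect of selecting the best items.** A simulation took the best two of four warnings per domain from a noisy pilot (200 / 4 = 50 people per domain; error variance of 0.5 per rating assumed). At s = 0.10 the domain test rejects 24% of the time, against 27.5% for two random items in the same simulation.

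**6. Testing against item variation instead.** With two items per level the F tests have (3, 4) and (5, 6) df, with .01 critical values of 16.69 and 8.75. The noncentrality is k·f² / (s²/2 + 1/n). For domain at f = 0.25, s = 0.1: 0.25 / 0.0075 = 33.3, giving 42% power. For s = 0.1, 0.2 and 0.3, power at f = 0.25 is 42%, 12% and 5% for domain and 66%, 20% and 8% for theme.

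**The case against.** The strongest reply is that a fixed-effects test holds its level for the items actually shown, and that the plan never writes that results will be reported as properties of a category. Aim 2 only says it will explore domain and theme, and the stated primary goal is the comparison of no warning, text, and text plus graphic. All of this stands, and it limits the point to the scope of the conclusions. It does not remove the point, because Aim 2 is worded in terms of categories, domain and theme are tested on the primary outcomes at the same .01 level as the arms, and nothing restricts the inference.

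The size rests on an item SD that the documents do not supply, and the range is wide. This also stands. The possibility of separate warning pairs per population roughly halves the domain figures at the lower assumed SDs, but they stay above 1% for any of the nonzero values shown.

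Pilot participants rate how well each item represents its domain or theme. That bears on whether the items are representative, but it supplies no error term.

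A reader might infer that one strong item is bound to produce a domain or theme finding. The documents do not support that: an item stronger by 0.2 SD does so only 7% to 11% of the time. Nor do they support reading this as a defect in the arm comparison. All arms draw on the same ads, and both warning arms use the same texts.

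**Conclusion.** The point holds as a limit on what the domain and theme tests can show. Under an item SD of 0.05 to 0.15 of the outcome SD, and with populations pooled, the nominal .01 level becomes roughly 6% to 56% for domain and 6% to 67% for theme when the claim is about the category. With separate warning pairs per population, the domain range is 3% to 32%. These figures assume independent item effects of equal SD, one value for ads and warnings alike, and balanced cells. They do not show that the planned tests are invalid for the selected items, that the sample size calculation is wrong, or that the arm contrasts are compromised.

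**What to change.** In the statistical considerations section:

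- State that domain and theme tests for H2A and H2B compare the selected warnings and ads, and will not be reported as effects of the domain or theme as a category. For H2A this is all the planned data allow, because the outcomes are measured once after both items.
- For H2B, add a mixed model with one row per participant and ad, and effects for participant, ad, text warning and, in the text plus graphic arm, graphic. Report item-level estimates and the between-item variance as a sensitivity analysis.
- State whether the pilot selection gives one set of warnings or one per population.

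The cost is a few sentences, one additional model on data already collected, and fewer category-level claims. Because a test against item variation has low power with two items per level, it should inform interpretation and not replace the planned test.
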